5.2.5 Qualitative interviews with NHS 24 Mental Health Hub service users

Qualitative insights from users of the NHS24 Mental Health Hub (MHH) will be gathered via Scottish lived experience networks including those linked to the National Suicide Prevention Leadership Group. We will work with the lived experience Study Advisory Group to identify a list of groups and organisations through which to reach individuals who accessed the NHS24 MHH between Oct 2019 and March 2020 to invite them to participate in a qualitative interview. Similar safe telephone screening, risk assessment and mitigation used with DBI service user participants will be employed for this group of participants, though these will use Qualitative Interviews Information Sheet and Consent Forms which are specific to NHS24 user participants.

The interviews will cover the individual's story from referral to exit from the NHS24 MHH including:

- Perceptions of what aspects of NHS24 MHH support, if any, were most beneficial in helping with study-specific outcomes (suicidal ideation, suicidal behaviour and self- harm, self-stigma and resilience) as well as contributory outcomes e.g. financial support
- Impact of other sources on above outcomes (life circumstances, informal support, other formal sources of support)
- Differences in experiences of other services accessed in distress/suicidality/self-harm
- Ways in which NHS24 MHH could be improved

5.2.6 Focus Groups with DBI staff

A total of seven focus groups will be held with DBI staff. Those undertaken at the pilot sites (six in total) will be held with DBI staff members, DBI Level 1 service representatives (police, ambulance and A&E) and management. An additional focus group will be undertaken with representatives of the DBI Central Team leadership and DBI Programme Board.

These focus group discussions will draw on early findings from surveys and interviews and issues raised by the SAG in relation to these to explore staff perceptions of:

- Impact(s) their intervention has on people presenting with suicidal thoughts, behaviour and/or self-harm
- Whether and how they can break down self-stigma and/or enable disclosure of the above
- What aspects of the DBI intervention model they provide contribute most to the above and why
- Contributing factors and barriers to their ability to support people with the above
- Unintended consequences of the DBI intervention
- Perceptions of whether and how follow-up DBI support for people with above problems would be beneficial
- Impact of Covid-19 on the above areas of interest

The draft focus group topic guide will be adapted in line with early findings and input from the Study advisory Group.

5.2.7 Health economic evaluation

To support the future commissioning of DBI, more evidence is needed on the care pathways of people who receive a DBI L2 intervention and their resource use within the health care, social care and third sector. In addition, for people who present in distress to GPs with suicidal ideation, suicidal behaviour and self-harm, there is no clear pathway for how they are currently managed within the health care system. This information is important if we seek to consider the impact the role of the DBI L2 route could have in the stages before unplanned access to care/support as well as following such care/support.

Design: Three concurrent phases of work will be conducted to address these key gaps in knowledge:

- Phase 1: To identify, measure and value DBI L2 delivery and individual health care, social care and third sector resource use over 12 months for DBI service users participating in the study
- Phase 2: To identify the existing care pathways for people with present to GPs in distress with suicidal ideation, suicidal behaviour and self-harm
- Phase 3: To collect health related quality of life data using a measure suitable for economic evaluation such as the Re-QoL as part of the DBI L2 individual survey

The GP route has been selected as the previous evaluation of DBI pilot sites indicated that at that time 40% of referrals were from primary care in-hours services. This indicates that DBI presents a possible complement to GP care and therefore, understanding the different resources required for the range of care pathway options open to GPs would be important in the future delivery of the DBI service.

Data Collection:

Phase 1: To measure the resource use of participants in the DBI L2 individual survey, we will collect data from participants on their other uses of health care, social care and third sector resources during the one month prior to referral & then at the immediate, 3- and 12-month points. This data will be collected via the same set of questionnaires used in the DBI L2 individual surveys in order to assess changes in resource use within the study participant group in the form of a before-and-after design.

As a minimum we will seek to collect data on

- Participant resource use of scheduled primary care (post-DBI): GP visits, mental health nurse, counsellor, medications, support groups, social prescribing
- Participant resource use of unscheduled primary care (post-DBI): emergency services, crisis team
- Participant employment status (post-DBI): full days unable to work due to distress

Phase 2: A sample of up to 20 GPs in participating NHS Boards who have been trained to provide L1 DBI will be surveyed to determine the typical care pathway for individuals in distress and at risk of self-harm. GPs will be identified using information provided by DBI Central. GPs will be sent an email by the study team including a PIS and asked if they would be willing to participate in an online survey and given the contact details of the researcher to follow up where consent can be taken before a link to the survey using REDCap₃₆ will be sent.

Data from the survey will be used to build the 'stylised' or typical care pathway options, these will be reviewed by the wider study team, SSG and SAG before costs are attached to the pathways. The resource use and costs of stylised care pathways for delivery of service will then be compared with the DBI pathway for people presenting with self-harm or suicidal ideation behaviour. These pathways will not consider individual level resource use.

Phase 3: The Recovering Quality of Life (Re-QoL)₃₂ health related quality of life measure, which has recently been developed specifically for people experiencing mental health difficulties, will be included in the suite of measures presented in the DBI L2 individual survey at the immediate, 3- and 12-month points. Health state utility values will be calculated at each time point to examine trends in the data.

5.3 Data analysis

Survey data analysis will include descriptive statistics and crosstabulation analysis with logistic regression if appropriate. We will compare demographic, referral source and presenting problem characteristics of survey respondents and non-respondents to assess the representativeness of the survey sample and whether any weighting adjustments are required.

Qualitative survey data will be coded using a staged content approach. Qualitative interviews will be summarised, charted and coded using QSR NVivo 12 and analysed with reference to techniques of framework analysis. Focus groups will be analysed using a framework matrix to explore themes across the data₃₇. We will explore any differences or similarities in the views of the DBI and control qualitative participants to assess any perceived impact of the DBI intervention, while paying attention to other contextual influences.

The data linkage analysis will assess whether the difference in frequency of unscheduled care in the year post intervention differs between DBI participants and the comparator group by doubly robust estimation₃₄ adjusted for unscheduled care received in the preceding year. This analysis will include adjustment for potentially confounding sociodemographic variables. Secondary analyses and likely zero inflation will be assessed. A full Statistical Analysis Plan will be developed prior to the identification of the comparator group. For the health economic analysis, units of each item for all care pathways and for participant resource use will be collated and presented along with unit costs which will be derived from local sources as well as those which are publicly available₃₈.

A summative data synthesis will be undertaken to draw together the above through a process of triangulation to develop evidence-based insights and conclusions. Throughout the study, the study team and the SAG, will meet to share thematic and theoretical insights from data collection and analysis and develop interpretive connections and points of synthesis. Policy and practice recommendations will be made.

6 STUDY SETTING

Data recruitment and administration of data collection (face to face, by telephone and/or online) will take place at each of the current six DBI service providers based in Inverness, Scottish Borders, Aberdeen and Lanarkshire. These teams are supportive of the study and are already experienced in similar recruitment and data collection procedures used successfully in the original evaluation. Participants will be recruited either at the community setting (e.g. DBI base, café, at home) in which they are meeting their DBI L2 worker or by telephone. Participants will have the option to complete surveys at the DBI base, online at home or on paper. Service user interviews will be either face to face by video or phone at an appropriate and safe place convenient to the participant. Staff focus groups will take place either face to face in a setting convenient to the staff or via a secure online meeting facility.

Staff focus groups will be face to face at a setting convenient to the participating staff members or online.

All other data collection (from GPs and NHS24 Mental Health Hub users) will be conducted online.

7 SAMPLE AND RECRUITMENT

7.1 Eligibility Criteria

The inclusion criteria for all study participants and the comparator groups are as follows:

DBI L2 individual quantitative surveys:

• All individuals accessing DBI in the first data collection year at participating DBI provider sites aged 16 years or over will be invited to participate.

DBI L2 service user qualitative interviews:

- Aged 16 years or over
- Agreed to be contacted for interview
- DBI service users who have experienced self-harm, suicidal thoughts or behaviour
- Referred to and received at least one supportive contact from a participating DBI L2 service
- Reported thoughts or acts of self-harm and/or suicide at any time within the past 12 months
- Level of literacy that allows informed consent, complete written records in English and participate in interviews

Comparator group:

- Those accessing NHS24 who were not referred to DBI because they accessed services prior to the roll out of DBI throughout Scotland via NHS24.
- People who contacted NHS 24 in October 2019 to March 2020 for mental health reasons.

NHS24 Comparator group interviews:

• Individuals who accessed NHS24 Mental Health Hub between Oct 2019 and March 2020.

DBI staff focus groups:

- DBI L2 staff members
- DBI Level 1 service representatives (police, ambulance and A&E)
- DBI local provider management
- DBI Central team leadership and DBI Programme Board members.

GP survey:

• GPs currently operating in Scotland with L1 DBI training.

The exclusion criteria are as follows:

DBI L2 individual surveys:

- DBI service users under the age of 16
- DBI service users for whom participation in the study is not deemed appropriate by DBI staff depending on individual circumstances

DBI service users qualitative interviews:

- DBI L2 service users who have responded to the quantitative survey but have not experienced self-harm, suicidal thoughts or behaviour
- Medically unfit for interview
- Unable to provide informed consent

- A level of literacy that is not sufficient to complete relevant assessment measures, engage with telephone contact and support or participate in interviews and/or are unable to provide contact details.
- Assessed to be at high or imminent risk of suicide before interview

7.2 Sampling

7.2.1 Size of sample and rationale

L2 DBI service users survey sample: maximum 2,700 (some attrition is expected as data collection progresses, n=2,700 for 1st and n=1350 for 2nd DBI surveys, n=675 for 3-4 month follow-up survey, n=330 for 1 year survey). DBI referral numbers suggest that each DBI provider will receive 1000 referrals in 1 year. In the original evaluation, participants were recruited in a similar way with just under half (46%) completing the first survey. For the L2 DBI individual survey in this study participant sample numbers are based on responses gained in the original DBI evaluation including likely attrition rates for follow-up surveys.

L2 DBI qualitative interviews: maximum 75 (some attrition is expected as data collection progresses). Over the course of the 12-month recruitment period an estimated 6000 individuals will be referred to the six participating DBI L2 services. DBI Programme routine data indicates that 45% of referrals to DBI L2 services experience suicidal thoughts, behaviour or self-harm. This suggests that 2700 referrals are potentially eligible for in-depth qualitative interviews. Our target sample size for in-depth qualitative interviews is 75 (3%) and is achievable with well-trained project staff and a £25 gift as compensation for the time to participate in the interviews.

Comparator group quantitative analysis: 2500. The comparator group of those accessing NHS24 who were not referred to DBI because they accessed services prior to the roll out of DBI throughout Scotland via NHS24 (since the inclusion of NHS24 as a L1 DBI provider in May 2020 it has become the main referral agency) will be selected from the Unscheduled Care Datamart. We will request Unscheduled Care Datamart records for 2018-2019 for people who contacted NHS 24 in October 2019 to March 2020 for mental health reasons.

For the comparator group quantitative analysis the sample size is based on 2500 people accessing the DBI L2 during the study period. Assuming the model: generalised linear model using binomial family and a logit link with dependent variable 'UCD use in the year after' and independent variables 'UCD use in the preceding year' and 'group' (DBI versus comparator). Estimating the following odds ratios for the model: intercept 0.80, group 0.70, UCD use in preceding year 2.0 and assuming the DBI group represents 10% of the total analysis sample and that the probability of UCD use in the preceding year is about 70% (estimate based on evaluation data) with alpha set to 0.05 we would have over 90% power to test that the odds ratio for 'group' is different to 1.

NHS 24 MHH qualitative interviews: 15. The sample of 15 interviews is based on the premise that the open invitation to participate through mental health lived experience networks will yield small numbers, however 15 interviews should be sufficient to provide the insights required for this study.

Stakeholder focus groups: 42 – 56 (6-8 per focus group). It is intended to hold one focus group per site. Given the relatively standardised nature of DBI it will not be necessary to hold multiple focus groups per site. 6-8 participants is a standard and recommended amount of people per focus group to aid discussion.

GP survey: 20. This should be sufficient to enable the generation of stylised pathways that are reflective of current practice. Recruitment of GPs to studies is very difficult due to their limited time so we would not wish to unnecessarily invite higher numbers to participate to minimise burden.

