The DBI programme is a unique approach to supporting those in distress who present to frontline services. It brings SG together with a DBI Central team, local NHS and voluntary DBI provider partnerships, national agencies (Primary Care, Police Scotland, Scottish Ambulance Service, Emergency Departments and NHS24), 3rd sector mental health organisations and University of Glasgow. Six delivery teams operate in four regions: one in each of Aberdeen, Borders, Inverness and three in Lanarkshire. In May 2019, DBI extended to include those aged 16-17. In June 2020, as a response to COVID-19, DBI was extended via NHS24 to gain national coverage. DBI comprises two levels. Level1 (L1) involves trained front-line staff (Primary Care, Police Scotland, Scottish Ambulance Service, Emergency Departments, Social Work and NHS24) offering a compassionate response to individuals in distress and enables referral to a Level2 (L2) service. At L2, individuals are contacted within 24 hrs and offered up to 14 days of community-based, person-centred support from trained staff. DBI explores the nature and cause of individual's distress and how they can manage it in the future. DBI service users co-create a Distress Management Plan (DMaP) with their L2 worker; the previous evaluation suggests many individuals were using their DMaP three months on from DBI intervention. Individuals are then sign-posted to and/or receive support to engage with appropriate follow-up support.

Intervention target length is currently set to two weeks (14 consecutive days) to ensure the service is brief but intervention length is tailored to individual needs. Most people (55%)

complete DBI L2 by 14 days, 25% by 21 days and 20% within a month or more. So far DBI has supported over 10,000 people. Over half (53%) of all individuals referred to DBI between November 2018 and January 2021, were assigned to at least one of the following presenting problem categories: suicidal thoughts (33%), self-harm (12%); thoughts of self-harm (8%); suicidal behaviour (6%); overdose (intentional) (10%). The deprivation profile of DBI service users (as indicated by SIMD) is skewed towards people living in more deprived areas with over half living in the two most deprived quintile areas and a fifth in the two least deprived quintile areas.

Pilot evaluation

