5.2.3 Qualitative interviews with individuals accessing DBI

Qualitative interviews with evaluation participants will be undertaken at 1 month, 3-4 months and 1 year following DBI L2 intervention. These in-depth face to face, video or telephone interviews will take place with evaluation participants who have agreed in their second survey (issued at their final DBI L2 session) to be contacted for interview, who have experienced suicidal thoughts, behaviour or self-harm on referral to DBI L2 and who have been assessed as eligible during the Safe Screening process outlined in section 7.3. The study team researchers undertaking the interviews will be ASIST (suicide prevention) trained. It is planned that up to six attempts will be made to contact those who have agreed to participate in interviews, however this will be reviewed with the Study Advisory Group.

The qualitative interviews will last for approximately one hour and will be semi-structured and focus on:

- The individual's DBI story from referral to exit from DBI and ongoing impact of the DBI intervention
- Perceptions of what aspects of DBI support, if any, were most beneficial in helping with studyspecific outcomes (suicidal ideation, suicidal behaviour and self-harm, self-stigma and resilience) as well as contributory outcomes e.g. financial support
- Impact of other sources on above outcomes (life circumstances, informal support, support from follow-up services that DBI sign-posted to and any other formal sources of support)
- Unintended consequences of the DBI intervention
- Differences in experiences of other services accessed in distress/ suicidality/self-harm
- Perceptions of whether and how support from DBI at the 3-4 month and/or year stage would be beneficial
- Impact of Covid-19 on own distress/suicidality
- Ways in which DBI could be improved

Participants will receive a £25 thank you voucher for their time following each interview.

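### The 75 interviews are justified as 3% of 2700 referrals, but only second-survey respondents can be interviewed, so the yield needed is about 10–12% if the stated shares carry over

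*Protocol*

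**What the plan says.** Section 7.2.1 of the protocol starts the interview calculation from all referrals: "an estimated 6000 individuals will be referred to the six participating DBI L2 services" over the 12-month recruitment period. It applies a 45% share with suicidal thoughts, suicidal behaviour or self-harm, taken from routine programme data, and concludes: "This suggests that 2700 referrals are potentially eligible for in-depth qualitative interviews". The target of 75 is expressed as 3% of that number and called achievable with trained staff and a £25 gift. The same section also describes 75 as a maximum, with some attrition expected.

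For the surveys, section 7.2.1 gives a maximum sample with "n=2,700 for 1st and n=1350 for 2nd DBI surveys".

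Section 5.2.3 confines interviews to "evaluation participants who have agreed in their second survey (issued at their final DBI L2 session) to be contacted for interview", and among these to people "who have experienced suicidal thoughts, behaviour or self-harm on referral to DBI L2". Sections 7.3.1, 7.4 and 7.5 describe the same route through the second survey, and section 7.1 makes agreement to contact an inclusion criterion. Section 7.1 words the clinical criterion differently: "Reported thoughts or acts of self-harm and/or suicide at any time within the past 12 months".

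The background in section 1 gives another share: "Over half (53%) of all individuals referred to DBI between November 2018 and January 2021" had at least one of a listed set of suicidality or self-harm presenting problems.

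**The concern.** The 3% is the only quantitative support for saying that 75 interviews can be obtained. Its denominator is every referral with the presenting problem, whether or not the person joins the study. The design cannot recruit from that group. It can recruit only from people who complete a second survey and agree there to be contacted, and section 7.2.1 itself expects far fewer of these.

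What is at stake is the planning of the qualitative strand, which serves the how-and-why research questions in section 4. A demand of 3% suggests ample slack. A demand several times higher makes the result depend on agreement, contact and screening rates that the protocol does not give. No power calculation or quantitative analysis is affected.

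The two eligibility wordings add to this. Status on referral and status over the past 12 months define different groups, so it is unclear which share should be applied to the second-survey respondents.

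**Working it through.** **Inputs (protocol)**
- Referrals: 6 providers × 1000 = 6000 (7.2.1)
- Share with suicidality or self-harm: 45% (7.2.1); 53% for November 2018 to January 2021 (section 1)
- Second surveys expected: 1350 (7.2.1)
- Interview target: 75 (7.2.1)

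**The protocol's own figure**
- 6000 × 0.45 = 2700, as stated.
- 75 / 2700 = 2.8%, rounded to 3%, as stated.

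**Restricting to people the design can reach**

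Pool = second-survey respondents × eligible share.
- At 45%: 1350 × 0.45 = 607.5, about 608; 75 / 607.5 = 12.3%; 2700 / 607.5 = 4.4.
- At 53%: 1350 × 0.53 = 715.5, about 716; 75 / 715.5 = 10.5%; 2700 / 715.5 = 3.8.

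Both lines assume that a share measured among referrals carries over to second-survey respondents.

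**How far the result depends on the share**
- If the same share applies to referrals and respondents, it cancels, and the ratio of the two pools is 6000 / 1350 = 4.4.
- In the limiting case where every second-survey respondent is eligible, 75 / 1350 = 5.6%, still twice the stated figure.

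**Losses after the second survey**

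Agreement to contact, the limit of six calls (5.2.3, 7.5) and the medical, consent, literacy and high-risk exclusions (7.1, 7.5) follow. No rates are given, so the retention figures below are assumptions.
- If 75%, 50% or 25% of 607.5 remain: about 456, 304 or 152 people, of whom 75 is 16%, 25% or 49%.
- If 30% agree and 30% of those are reached and pass screening: 607.5 × 0.3 × 0.3 = about 55. With 70% at both steps: 607.5 × 0.7 × 0.7 = about 298.
- Break-even is a combined yield of 12.3%, for example about 35% at each of the two steps (0.35 × 0.35 = 0.123).

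**The case against.** The best defence is that nothing is miscalculated. Both 2700 and 3% reproduce, and the sentence speaks only of referrals that are potentially eligible, which is a fair count of people with the presenting problem before consent. That stands as far as the 2700 goes. It does not rescue the 3%, which is used as the recruitment fraction behind the feasibility statement.

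A second defence is that 608 is not a protocol figure. This also stands. It needs the 45% to hold among respondents, and the 12-month criterion in section 7.1 could admit a larger share. For that reason 12% is not a floor.

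Third, 75 is already called a maximum with attrition expected. But it is also called the target and defended as achievable, so its status is unclear.

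Stronger readings are tempting but unsupported:
- A reader might infer that the target will be missed. That follows only at the low corner of assumed rates; most of the assumed values above leave more than 75.
- A reader might apply the survey attrition to the interviews: 75 × 675/1350 = about 38 at 3–4 months and 75 × 330/1350 = about 18 at one year. The protocol does not equate the two. Interviews carry a larger voucher (£25 against £10), up to six contact attempts and an aim to keep the same interviewer.
- A reader might take 45% and 53% as contradictory. The 53% has a stated period and category list and the 45% has neither, so a conflict is not shown.

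**Conclusion.** The point holds as a defect in the justification. The pool in section 7.2.1 is not one that the design can recruit from, and the stated 3% understates the yield required about fourfold: 12.3% at a 45% share, 10.5% at 53%. These figures rest on 1350 second surveys being obtained and on the share among referrals carrying over to respondents. They are stated before refusal, failed contact and screening.

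The documents show neither that 75 is attainable nor that it is out of reach, so the feasibility statement is unsupported rather than refuted.

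The difference in eligibility wording between sections 5.2.3 and 7.1 is real and changes who may be interviewed. A reader might think that the research questions settle it, but they do not. One covers current or previous suicidality without a 12-month limit, and another concerns people who present to DBI with it. The consequence is modest and confined to the qualitative strand.

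**What to change.** In section 7.2.1, replace the pool with expected second-survey respondents multiplied by the eligible share: about 600–700 people, of whom 75 is about 10–12%. State that the share is assumed to carry over from referrals, and that agreement to contact, the call limit and safe screening reduce the pool further. Say whether 75 is a target or a ceiling.

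Reconcile the interview eligibility wording in sections 5.2.3 and 7.1 into one definition, and take the eligible share from that definition.

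The cost is protocol wording only. No data collection or analysis changes, but the feasibility figure becomes less favourable than the one now printed.
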